#### 3.5.1 Adverse Events

AEs will be graded by the investigator according to the CTCAE version 5 and coded using MedDRA. AE data will be reported in tables and listings. Summaries of AE by appropriate MedDRA terms, toxicity grade, and seriousness and relationship to study treatment will be presented, as well as summaries of AEs leading to death and premature withdrawal from study treatment. The number and percentage of participants who experienced any AE, SAE, treatment-related AE, and treatment-related SAE will be summarized according to worst toxicity grades. The summaries will present AEs both on the entire study period and by cycle (Cycle 1 and Cycles beyond 1). When a priming dose is used, the full 42 day period will be reported separately, instead of Cycle 1. Listings of DLTs and deaths will be provided.

A similar approach will be used for irAEs.

#### 3.5.2 Laboratory Data

Details of the laboratory tests can be found in [Appendix 10.2 of the protocol](#).

## 4. ANALYSIS SETS (POPULATIONS FOR ANALYSIS)

Data for all participants will be assessed to determine if participants meet the criteria for inclusion in each analysis population prior to unblinding and releasing the database and classifications will be documented per standard operating procedures.

**Table 1. Analysis Sets**

Participant Analysis Set	Description
Full Analysis Set (FAS)	All enrolled participants.

Participant Analysis Set	Description
Safety Analysis Set (SAS)	All enrolled participants who receive at least 1 dose of study intervention. Unless otherwise specified the safety analysis set will be the default analysis set used for all analyses.
Per Protocol Analysis Set	All enrolled participants who do not have major protocol deviations during the course of the study
DLT Evaluable Set	All enrolled participants who had at least 1 dose of study treatment and either experienced DLT or do not have major protocol deviations during the DLT observation period and received either 100% of dosing in cycle 1 (no priming regimen) or 100% of dosing in cycle 1 and cycle 2 (priming regimen)..
mITT Population	All enrolled participants who have received at least 1 dose of study medication; have a baseline assessment and at least 1 post baseline assessment;
Response Evaluable set	The response evaluable population will include all participants who received at least one dose of study treatment and had measurable disease at baseline and at least one post baseline disease assessment.
PK Parameter Set	All enrolled participants treated who do not have protocol deviations influencing PK assessment and have sufficient information to estimate at least 1 of the PK parameters of interest.
PK Concentration Set	All enrolled participants who are treated and have at least 1 analyte concentration above the lower limit of quantitation.

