Visit Identifier Abbreviations used in this table may be found in Appendix 17	Screening	Treatment Period									EOT	4-week Follow- up	90-day Follow- up for irAEs	Notes
		Cycle 1 =28 days				Cycle ≥ 2 (28 days)								
Study Day	-28 to -1	1	2 ^a	8	15	16 ^a	22	1	8 ^b	15				
 Additional visit window may be allowed after discussion and agreement between investigator and sponsor. 
a: End of inpatient observation (PK, ECG, vital signs).
 
b: This D8 visit is only applicable for Cycles 2 and 3, whereas, C3D8 is applicable for PK/PD and ECG only.

Visit Window (days)		± 2		± 2	± 2			± 2	± 2	± 2		± 7	± 7	
Study Intervention														
PF-07260437		X (priming dose)		(X ^c)	X			X		X				
 C1D1 is priming dose and C1D15 is full/maintenance dose. c: A 2-step priming may be considered on C1D1 and C1D8. See Section 4.1 for additional information.

Table 3. Study Schedule of Assessments – Part 1 With Priming

Visit Identifier Abbreviations used in this table may be found in Appendix 17	Screening	Treatment Period									EOT	4-week Follow- up	90-day Follow- up for irAEs	Notes
		Cycle 1 =28 days												
Study Day	-28 to -1	1	2 ^a	8	15	16 ^a	22	1	8 ^b	15				
 Additional visit window may be allowed after discussion and agreement between investigator and sponsor.
Visit Window (days)		±2	±2	±2		±2	±2	±2	±2	±2		±7	±7	
a: End of inpatient observation (PK, ECG, vital signs).
 
b: This D8 visit is only applicable for Cycles 2 and 3, whereas, C3D8 is applicable for PK/PD and ECG only.

Premedication		(X)	(X ^d)	(X)			(X)		(X)					
 Prophylactic premedication is not allowed during the DLT evaluation period during initial dose escalation. However, if the participant experiences an infusion related reaction (IV), allergic reaction, significant injection site reaction, CRS, fever/chills, allergic reaction, nausea/vomiting, hypotension, or pain, appropriate treatment should initiate and premedication as prophylaxis may be considered for subsequent injections as well as for new participants. See Section 6.1.1.1 for additional information. d: Only applicable to 2-step priming

Table 3. Study Schedule of Assessments – Part 1 With Priming

Visit Identifier Abbreviations used in this table may be found in Appendix 17	Screening	Treatment Period									EOT	4-week Follow- up	90-day Follow- up for irAEs	Notes

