All participants will undergo up to 28 days of screening prior to first dose. Eligible participants will then receive study intervention for up to 2 years, or until disease progression defined by irRECIST, unacceptable toxicities, a decision by the participant (withdrawal of consent or no longer willing to participate) or investigator to discontinue treatment, or study termination. Note: If a participant is classified as having PD during an on-treatment tumor assessment, then confirmation of PD by a second scan in the absence of rapid clinical deterioration is required per irRECIST ([Appendix 13](#)).

Any additional treatment beyond 2 years shall be discussed and approved by the sponsor. After EOT, all participants will complete a 28-day post-treatment follow-up visit for AEs. All participants will be contacted by telephone approximately 90 days post treatment to assess late irAEs. Participants in Part 2 dose expansion cohorts will be contacted by telephone approximately every 3 months for survival data collection until end of trial (2 years from last participant first dose), unless otherwise notified by the sponsor.

A participant is considered to have completed the study if he/she has completed all phases of the study including the last scheduled procedure shown in the [SOA](#) including OS, if applicable. OS follow-up should not continue after end of the study ([Section 4.4](#)).

During treatment with study intervention, all cycles will be 28 days in length. Every effort should be made to administer study intervention on the planned dose and schedule. In the event of significant toxicities, dosing may be interrupted, modified, or discontinued as described in [Section 6.5](#) and [7.1](#).

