4.3.6. Dose Limiting Toxicity (DLT) Definition

A participant is classified as DLT evaluable if they either 1) receive all the planned doses of the study intervention and have received all scheduled safety assessments during the DLT observation period or 2) have experienced a DLT. If a participant fails to meet these criteria, they may be replaced. The sole exception to criterion 1) is if the participant has missed a minority of safety assessments due to emergency situations (eg, site accessibility issues, inability to go to an external lab, etc). In such cases, the Dose Level Review Committee may judge the participant evaluable, depending on the abundance of the available data.

DLT observation period: For the purpose of dose escalation, the DLT observation period for SC or IV dosing without priming will be 28 days including laboratory results obtained on the morning of Day 29 in each participant. The DLT period for dosing with priming will extend to include the duration of priming doses and 2 full doses (eg, if a single priming dose is administered 2 weeks prior to the first full dose, the DLT evaluation period will be 42 days (14 days plus 28 days) including laboratory results obtained on the morning of Day 43 (C2D15).

Any of the following treatment-related AEs occurring during the DLT observation period that in the opinion of the investigator cannot be reasonably attributed to the participant's underlying disease, concomitant medications or preexisting conditions are considered DLTs. Severity of AEs will be graded according to CTCAE version 5.0, with the exception of CRS, which will be graded according to the ASTCT CRS Consensus Grading for CRS (Appendix 11). For those events involving a worsening of a baseline abnormality, a DLT must represent a clinically significant (in the opinion of the Investigator after discussion with the sponsor) shift from baseline.

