6.1.1.2. SC Administration

Qualified and trained investigational site personnel will administer PF-07260437 to participants by SC injection. PF-07260437 will be administered at a flat dose via SC injection Q2W at 28-day cycles (on Day 1 and Day 15) until the participant meets one of the study intervention discontinuation criteria (See [Section 7.1](#)). Participants should have SC injections in the abdomen with preference to the lower quadrants when possible. For participants receiving 2 or more SC injections, PF-07260437 should be administered in 2 or more different quadrants of the abdomen (with preference given to the lower quadrant when possible); 1 or 2 injections per quadrant. The injection can be rotated with each administration for participant comfort. Refer to [Appendix 14](#), for details on administration of multiple injections to the abdomen.

Each injection volume may be up to 2 ml in volume. If an institutional policy sets a maximum volume <2 ml, the number of injections may be increased to ensure that the correct volume is administered. Refer to the IP Manual for specific instructions on the handling and preparation of study treatment.

Refer to [Table 7](#) for required inpatient observation stays following PF-07260437 administration.

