#### 2.1. Study Objectives, Endpoints and Estimands

##### 2.1.1 Primary Estimand(s)

###### Primary Estimand (DLT) for Part 1:

DLT rate estimated based on data from DLT-evaluable participants during the DLT-evaluation period (28 days for regimen without priming; 42 days for the regimen with priming (priming doses plus 2 full doses)) in Part 1.

Variable: Occurrence of DLTs.

Analysis population:

For the dose escalation without priming, DLT-evaluable participants defined as participants:

- who receive at least 1 dose of study treatment and experience DLT during the DLT-evaluation period (28 days),

OR

- who complete the DLT-evaluation period without DLT. Participants without DLTs who withdraw from study treatment before receiving at least 2 full doses of study drug for reasons other than treatment-related toxicity are not evaluable for DLT.

For the dose escalation with priming, DLT-evaluable participants defined as participants:

- who receive at least 1 dose of study treatment and experience DLT during the DLT-evaluation period (priming doses plus 2 full doses, eg, 42 days),

OR

- who complete the DLT-evaluation period without DLT. Participants without DLTs who withdraw from study treatment before receiving at least the priming dose and 2 full doses of study drug for reasons other than treatment-related toxicity are not evaluable for DLT.

Population-level summary measure: DLT rate defined as the number of DLT-evaluable participants with DLTs in the DLT-evaluation period divided by the number of DLT-evaluable participants in the DLT-evaluation period.

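### For the primed regimen, the SAP's DLT Evaluable Set asks for a dose that nominally falls after the 42-day DLT window, so DLT-free completers can be classed as not evaluable

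*SAP*

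**What the plan says.** SAP Table 1 (Analysis Sets) admits treated participants to the DLT Evaluable Set if they had a DLT, or if they had no major protocol deviation in the DLT observation period and met a dosing condition. For the priming regimen that condition is "100% of dosing in cycle 1 and cycle 2 (priming regimen". Without priming it is all Cycle 1 dosing.

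The window is defined elsewhere by doses and days:

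- SAP 2.1.1 gives "42 days for the regimen with priming (priming doses plus 2 full doses". A participant without a DLT is evaluable if among those "who complete the DLT-evaluation period without DLT". The only exclusion is withdrawal, for reasons other than treatment-related toxicity, before the priming dose and two full doses.
- Protocol 4.3.6, for a single priming dose two weeks before the first full dose, says "the DLT evaluation period will be 42 days (14 days plus 28 days) including laboratory results obtained on the morning of Day 43 (C2D15". Its dosing requirement concerns planned doses in the observation period.
- The DLT Evaluable Set in Protocol 9.2 has no cycle-based dosing clause.

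For the schedule, Protocol 4.1 says "all cycles will be 28 days in length", Protocol 6.1.1.2 gives dosing "via SC injection Q2W at 28-day cycles (on Day 1 and Day 15", and the with-priming schedule in Protocol 1.3.2 says "C1D1 is priming dose and C1D15 is full/maintenance dose".

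SAP 3.1 and 6.1.1 assign MTD determination to the Per-protocol set, which Table 1 defines by the absence of major deviations over the whole study.

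**The concern.** Table 1 counts cycles, while the estimand counts doses in a window. Without priming the two agree, because both Cycle 1 doses lie in the 28-day window. With priming they differ by one full dose. Someone who takes every in-window dose, has no DLT, and then progresses, withdraws or has dosing held at C2D15 has given all the information the DLT rate needs, yet fails Table 1.

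At stake is the denominator of a Part 1 primary estimand in cohorts of about three. If the Table 1 set is used, DLT-free participants can be lost for something that happens after the observation period, or be replaced without need.

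**Working it through.** **1. The plan's own window.** Single priming dose on Day 1, first full dose on Day 15: 14 + 28 = 42 days. This reproduces the figure in Protocol 4.3.6 and SAP 2.1.1.

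**2. Dose days.** 28-day cycles, doses on Days 1 and 15 of each cycle:

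| Dose | Study day | In Days 1–42? |
|---|---|---|
| C1D1, priming | 1 | yes |
| C1D15, full dose 1 | 15 | yes |
| C2D1, full dose 2 | 28 + 1 = 29 | yes |
| C2D15, full dose 3 | 28 + 15 = 43 | no |

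Protocol 4.3.6 itself labels Day 43 as C2D15 and adds only that morning's laboratory results. Table 1 thus requires three full doses where the estimand requires two.

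**3. Limits of the mismatch.**

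- The visit window of ±2 days in Protocol 1.3.2 puts C2D15 on Days 41–45, so an early dose could fall inside the window.
- Two-step priming on C1D1 and C1D8, with the first full dose still on C1D15, gives the same 42 days.
- If a longer priming scheme moved the first full dose to C2D1, the window would be 28 + 28 = 56 days and C2D15 would lie inside it.

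**4. One participant, three definitions.** Priming, C1D15 and C2D1 given; no DLT to Day 42; scheduled assessments done; no major deviation; C2D15 not given.

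- SAP 2.1.1: evaluable.
- Protocol 4.3.6: evaluable.
- SAP Table 1: not evaluable.

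**5. Crude DLT rate.** With x DLTs among n, and one DLT-free completer removed and not replaced, the rate goes from x/n to x/(n − 1):

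- 1/6 = 16.7% becomes 1/5 = 20.0%
- 2/6 = 33.3% becomes 2/5 = 40.0%
- 1/3 = 33.3% becomes 1/2 = 50.0%
- 0/3 becomes 0/2, with the rate unchanged at 0%

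**6. How often.** The documents give no rate for missing C2D15. If a share q of DLT-free completers misses it (assumed), the chance of losing at least one of n is 1 − (1 − q)^n:

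| q (assumed) | n = 3 | n = 6 |
|---|---|---|
| 5% | 14.3% | 26.5% |
| 10% | 27.1% | 46.9% |
| 20% | 48.8% | 73.8% |

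**7. Can the effect on the 25% overdose limit be stated?** Protocol Appendix 9 gives the prior form only for the regimen without priming, with no values for p* or d*. At d = d* the slope drops out and logit(π) has prior mean logit(p*) and SD 2. Over assumed p* of 0.10 to 0.33, the posterior probability that π exceeds 0.33 is:

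- 1/6: 0.100 to 0.176
- 1/5: 0.147 to 0.247
- 1/4: 0.214 to 0.344

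Removing one participant does not cross 0.25 anywhere in this range. Removing two crosses it at p* = 0.20, 0.25 and 0.33 (0.282, 0.308, 0.344) but not at 0.10. The result follows the assumed p*, and this is not the prior named for the primed regimen.

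**The case against.** **Which set governs.** SAP 3.1 and 6.1.1 use the Per-protocol set for the MTD, and SAP 2.1.1 carries its own, correct population for the DLT rate. On that view the Table 1 set feeds nothing. This stands as a limit on the consequence. It does not remove the conflict: the estimand's denominator is DLT-evaluable participants, and the SAP now defines that group in two ways.

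**The 25% limit.** A reader might infer that one dropped participant pushes a dose over the limit and so distorts the primed MTD. The documents do not support that. SAP 3.1 gives the primed regimen a MAP prior built on the unprimed Part 1 data. That prior, p* and d* are not stated, and SAP 2.2 refers to a technical supplement for details.

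**Direction.** A reader might also infer that the DLT rate can only rise. That depends on how Table 1's sentence is grouped. If the dosing condition applies to both branches, a participant who stops dosing because of a DLT is dropped too, and 1/6 could become 0/5. The natural reading keeps participants with a DLT in, but the wording does not settle it.

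**Replacement.** Protocol 4.3.6 lets non-evaluable participants be replaced. In the 1/6 example the count then becomes 1/6 or 2/6 rather than 1/5, at the cost of one more participant.

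**Timing and caution.** Classification is barely delayed, since the window already takes in laboratory results from the morning of C2D15. On the natural reading the error overstates toxicity, which is the cautious side for overdose control. Both points are fair and lower the stakes.

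**Conclusion.** The conflict is real and stands in the current text. For single priming on the nominal schedule, Table 1 requires one full dose more than the DLT window contains, and it classes as not evaluable some participants whom SAP 2.1.1 and Protocol 4.3.6 count.

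The supported size is 3 to 17 percentage points on the crude DLT rate per unreplaced participant in the examples with at least one DLT (1/6 to 1/5 and 1/3 to 1/2 being the extremes), and no change where there are none. This assumes that priming is used, that the Table 1 set is the one applied, that participants with a DLT always stay in, and that a DLT-free completer misses C2D15. No bias in the primed MTD and no crossing of the 25% limit can be claimed from these documents.

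**What to change.** In SAP Table 1, replace the cycle-based dosing clause with the SAP 2.1.1 definition and group it explicitly:

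- (a) received at least one dose and had a DLT in the DLT observation period; or
- (b) completed that period without a DLT and without a major protocol deviation in it, excluding anyone who withdrew before the planned priming dose(s) and two full doses for reasons other than treatment-related toxicity.

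Do not make C2D15 a condition when it falls outside the window. Simply requiring two full doses of every DLT-free participant would not match SAP 2.1.1, which does not exclude those who withdraw earlier for treatment-related toxicity.

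Reconcile (b) with Protocol 4.3.6, which asks for all planned doses and scheduled safety assessments in the period. State in SAP 3.1 and 6.1.1 that this set, not the whole-study Per-protocol set, feeds the DLT rate, the BLRM and the MTD determination. Protocol 9.3.2 also names the Per-protocol set and should be aligned.

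The cost is a few lines of text. It adds no participants, visits or procedures, and should be done before any primed cohort is classified.
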